5.2 Treatment Regimen

The maximal dosage of topiramate in this study will be 200 mg/day orally in two divided doses, based on prior evidence of the efficacy and greater tolerability of this dosage (Kranzler, Covault et al. 2014). Although a 300-mg dosage of topiramate has been used most commonly to treat AD, we will use a lower dosage to reduce adverse effects. We will use a six-week titration period (see Table 1 below), which we found in our completed topiramate study to be well tolerated. We will reduce the dosage of topiramate by one-half for anyone with a creatinine clearance <70 mL/min/1.73 m².

Table 1. Topiramate or Placebo Dose Titration/Taper Schedule

	Medication Dispensed	Morning Dose	Evening Dose	Total Daily Dose
Screening Visit	Week 0	No medication	No medication	0 mg
Visit 1 Baseline	Week 1	No medication	25 mg	25 mg
Visit 2	Week 2	25 mg	25 mg	50 mg
Visit 3	Week 3	25 mg	50 mg	75 mg
Visit 4	Week 4	50 mg	50 mg	100 mg
Visit 5	Week 5	50 mg	100 mg	150 mg
Visit 6	Weeks 6 and 7	100 mg	100 mg	200 mg
Visit 7	Weeks 8 and 9	100 mg	100 mg	200 mg
Visit 8	Weeks 10 and 11	100 mg	100 mg	200 mg

CONFIDENTIAL

This material is the property of the University of Pennsylvania. Do not disclose or use except as authorized in writing by the study sponsor

Visit 9	Week 12 and 6- day Taper	100 mg	100 mg	200 mg
		Reduce dose by 50 mg every 2 days over 6 days: 150 mg for 2 days, 100 mg for 2 days, 50 mg for 2 days, then D/C		
Visit 10	Week 14	No medication	No medication	0 mg
Visit 11 (3-Month Follow-up)	Week 24	No medication	No medication	0 mg
Visit 12 (6-Month Follow-up)	Week 36	No medication	No medication	0 mg

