Table 2. Schedule of Study Assessments and Procedures

Assessment or Procedure	Visit 0 Screen Wk 0	Visit 1 Baseline Wk 1	Visits 2-5 Wks 2-5	Visit 6 Wk 6	Visits 7 & 8 Wks 8 & 10	Visit 9 (Wk 12) & Taper	Visit 10 Endpoint Wk 13	Visits 11&12 Follow-up Wks 24 & 36
ALL VISITS								
Breathalyzer, weight & vitals	X	X	X	X	X	X	X	X
SCREENING								
Informed Consent	X							
Med Hx & Physical Exam	X							
LABORATORY TESTS								
Chemistry Panel, CBC, DNA	X							
GGTP, %dCDT	X			X			X	X
Bicarbonate	X			X				
Urinalysis & urine toxicology	X							
Urine pregnancy test for women of childbearing potential	X	X	X (Visit 5 only)		X (Visit 7 only)	X		
ASSESSMENTS								
SORT	X							
Demographic Interview	X							
Locator information	X							
SCID (with DSM-5 AUD)	X							
SCID (only DSM-5 AUD)							X	X
FHAM	X							
TLFB	X	X	X	X	X	X	X	X
SIP		X					X	X
PHQ-9		X	X	X	X	X	X	X
Digit Span	X						X	X
FTND	X						X	X
COWA	X						X	X
SF-12		X					X	X
MINI 6.0 (Section B only)	X	X	X	X	X	X	X	X
CIWA-AR	X	X	X	X	X	X	X	X
AUQ		X					X	X
CSM		X						
ISI		X	X	X	X	X	X	X

GGTP=gamma-glutamyltranspeptidase, %dCDT=% disialotransferrin, SORT= Slosson Oral Reading Test, SCID=Structured Clinical Interview for DSM-IV, AUD=Alcohol Use Disorder, FHAM=Family History Assessment Module, TLFB=Timeline Follow-back Interview, SIP=Short Index of Problems, PHQ-9=Patient's Health Questionnaire, FTND=Fagerstrom Test for Nicotine Dependence, COWA= Controlled Oral Word Association Test, SF-12=Short Form Health Survey, MINI=Mini International Neuropsychiatric Interview, CIWA-Ar=Clinical Institute Withdrawal Assessment for Alcohol-revised, AUQ=Alcohol Urge Questionnaire, CSM= Composite Scale of Morningness, ISI=Insomnia Severity Index, **Performed only if sub-study visit is not done on same day as main study visit, when these assessments are routinely done.

CONFIDENTIAL

This material is the property of the University of Pennsylvania. Do not disclose or use except as authorized in writing by the study sponsor

Assessment or Procedure	Visit 0 Screen Wk 0		Visit 1 Baseline Wk 1	Visits 2-5 Wks 2 through 5	Visit 6 Wk 6		Visits 7 & 8 Wks 8 & 10	Visit 9 (Wk 12) & taper	Visit 10 Endpoint Wk 13	Visits 11&12 Follow-up Wks 24 & 36
CLINICAL TREATMENT										
Dispense Study Medication			X	X	X		X	X		
Return Study Medication				X	X		X	X	X	
Adverse Events Checklist			X	X	X		X	X	X	X
Measures of Treatment Received			X	X	X		X	X	X	X
Medical Management			X	X	X		X	X	X	
IVR Reports/Daily Diary			X	X	X		X	X		

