- *Locator information*: The research coordinator will select subject locators on the basis of relationship to the subject, duration and current status of relationship, frequency of contact with the subject, and willingness to participate. Locators are contacted when efforts to reach a subject are unsuccessful, which enhances retention of subjects in treatment and data collection.
- *The Structured Clinical Interview for DSM-4 (SCID)* will be used to classify subjects according to the presence or absence of standard psychiatric disorders according to DSM-criteria. The alcohol use disorder criteria will be modified to permit a DSM-5 diagnosis as well.
- *The International Neuropsychiatric Interview 6.0 (Mini 6)*: Suicidal risk will be assessed using the MINI Suicidality section (B) at each study visit and, if rated greater or equal to 9 (i.e., clinically significant suicidal ideation), the physician will be consulted to decide on the appropriate clinical management.
- *The Family History Assessment Module* (Rice, Reich et al. 1995) systematically queries the subject about the presence of an alcohol use disorder (AUD) in relatives. The subject will provide information concerning parents' and siblings' history of alcohol use without their being identified.
- *The Timeline Follow-back (TLFB)* (Sobell and Sobell 1992) will be used to estimate past 90-day drinking at intake and at every treatment visit going back in time from the last assessment. This interview procedure will provide quantity/frequency of alcohol consumption data for each day during the period prior to the interview. The TLFB is reliable and valid when used by trained interviewers. However, it is less useful than daily measures for detecting patterns of alcohol consumption that vary on a day-to-day basis (Carney, Tennen et al. 1998; Searles, Helzer et al. 2000).
- *Controlled Oral Word Association Test (COWA)* is a verbal fluency test that takes approximately 5 minutes to administer and measures spontaneous production of words beginning with a designated letter (Ruff, Light et al. 1996). This measure will be used to examine the effects of topiramate on verbal fluency.
- *Wechsler Adult Intelligence Scale-Third Edition Digit Span subtest* (Wechsler 1997) will be used to assess verbal working memory and explore the potential effects of topiramate on verbal working memory.

CONFIDENTIAL

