6.4.1 Visit 9 (Week 12 and taper)

The study nurse will dispense study medications as shown in Table 1. At this visit (+/- 4 days), the subject will receive 1 more week of 100 mg BID (enough study medication to complete a total of 84 days on study medication) and the 6-day study medication taper (to reduce the dose by 50 mg every 2 days over 6 days: 150 mg for 2 days, 100 mg for 2 days, 50 mg for 2 days, then discontinue it). In the event that scheduled visits change or the subject's dosage is adjusted by the study physician, medication will be mailed via a UPS or Fedex to the subject, to ensure that they have enough medication to get them to their next scheduled visit. The study physician will approve all medication mailed to subjects and the study nurse or physician will document the medication dispensed via mail and call to instruct the subject on how the medication should be taken and to document all AEs. Study staff will also document whether mailed medication was received by the subject.

At this visit, the subject's BrAC, weight, and vital signs will be measured. Subjects will be asked not to drink before coming to the scheduled visits. Subjects will be asked to complete a breathalyzer test. If a subject's breath alcohol concentration is $\geq 0.02\%$, an investigator will evaluate whether the subject is too impaired to complete the study assessments. The study visit may be completed at the discretion of the investigator. If the subject is deemed to be unable to complete assessments, the investigator may ask the subject to wait until his or her blood alcohol level decreases or if that is not feasible to return the next day after having consumed no alcohol. Prior to discharge from the TRC, a clinician will assess the subject to ensure that it is safe for the subject to leave. Study staff will complete the following assessments with all subjects (the exception being that only for women of childbearing potential, will study staff obtain a urine sample for a pregnancy test). Subjects who are deemed suitable for assessment will then complete questionnaires and be interviewed by the study nurse about their concomitant medications, adverse events, protocol compliance, and MM intervention. For women of childbearing potential, study staff will obtain a urine sample for a pregnancy test.

Study staff will also administer the following assessments, as described above:

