6.5 Visit 10 (Week 13; Endpoint Visit)

At the end of treatment, week 13 (+/- 4 days) we will repeat the research assessments and will query the subject as to his or her belief regarding their treatment condition using the Medication Questionnaire (MED-Q). Blood samples for measurement of serum GGTP and %dCDT will be obtained to assess the validity of self-reported drinking. Subjects will be asked not to drink before coming to the scheduled visits. Subjects will be asked to complete a breathalyzer test. If a subject's breath alcohol concentration is $\geq 0.02\%$, an investigator will evaluate whether the subject is too impaired to complete the study assessments. The study visit may be completed at the discretion of the investigator. If the subject is deemed to be unable to complete assessments, the investigator may ask the subject to wait until his or her blood alcohol level decreases or if that is not feasible to return the next day after having consumed no alcohol. Prior to discharge from the TRC, a clinician will assess the subject to ensure that it is safe for the subject to leave. Study staff will complete the following assessments with all subjects (the exception being that only for women of childbearing potential, will study staff obtain a urine sample for a pregnancy test). Subjects who are suitable for assessment will then complete questionnaires and be interviewed by the study nurse.

All subjects will be asked to complete an end-of-treatment evaluation and to complete all scheduled assessments to facilitate intent-to-treat (ITT) analyses. All subjects will be informed of these procedures prior to study enrollment. Subjects will be compensated \$50 for completing the end-of-treatment visit. Subjects who decide to terminate the study prior to visit 10 will also receive payment upon completion of the end-of-treatment procedures and 3- & 6-month follow-up visits. For subjects who withdraw early and do not wish to continue with study visits/procedures, all end-of-treatment procedures will be administered at the time of withdrawal. These subjects will also be asked to undergo in-person or telephone follow-up at the end-of-treatment for collection of the remaining treatment-phase Timeline Follow-back data.

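### COWA and Digit Span, collected to show topiramate's effect on verbal fluency and working memory, are not scheduled at any visit clearly on maintenance dosing, and Visit 10 has two different dates

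*Combined protocol and SAP*

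**What the plan says.** Section 6.2 gives both tests a drug-related purpose. For COWA: "This measure will be used to examine the effects of topiramate on verbal fluency". Digit Span is to assess verbal working memory and "explore the potential effects of topiramate on verbal working memory".

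Table 2 marks each test in three columns only: screening, Visit 10, and Visits 11 and 12 (the Digit Span row reads "Digit Span X X X"). The visit lists agree. Neither test appears in section 6.4 (Visits 2-8) or 6.4.1 (Visit 9). Both appear in 6.5 (Visit 10) and 6.8 (follow-up).

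The date of Visit 10 differs between places:

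- Table 2 column heading: "Visit 10 Endpoint Wk 13".
- Section 6.5: "At the end of treatment, week 13 (+/- 4 days) we will repeat the research assessments".
- Section 5.2, Table 1: "Visit 10 Week 14 No medication No medication 0 mg".

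On dosing, section 6.4.1 has Visit 9 supply "enough study medication to complete a total of 84 days on study medication", followed by a six-day taper: "150 mg for 2 days, 100 mg for 2 days, 50 mg for 2 days", then stop.

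**The concern.** A test meant to show what a drug does to performance is most informative while subjects take the drug at its intended dosage. Table 1 schedules several weeks at 200 mg/day, and no COWA or Digit Span is placed clearly inside them. The one end-of-treatment administration falls around the taper on one dating of Visit 10 and after it on the other.

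Two things follow if cognitive effects track exposure. The topiramate-placebo difference at Visit 10 is diluted, and subjects tested on different days of the window contribute different exposures to one comparison. Section 1.5 makes the question relevant: it lists word-finding, memory and concentration difficulties, reports cognitive adverse effects in 28% against 10% on placebo in migraine studies, and says tolerability problems seen in some studies were transient or resolved on stopping the drug. Testing late in the taper would tend to miss such effects.

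**Working it through.** **Inputs.** Table 1 dispensing blocks and doses; the taper in 6.4.1; the +/- 4-day windows in 6.4.1 and 6.5; the 21-hour half-life in section 1.2.

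**Day count (Visit 1 = day 1).** Visits 1-5 cover 5 x 7 = 35 days, Visits 6-8 cover 3 x 14 = 42, and Visit 9 covers 7. The total is 35 + 42 + 7 = 84, which reproduces the protocol's 84 days. Scheduled 200 mg/day therefore runs from day 36 to day 84 (49 days), the taper from day 85 to day 90, and 0 mg from day 91.

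**Visit days.** Start of week w = 7(w - 1) + 1. This gives day 78 for Visit 9 (week 12), day 85 for week 13 and day 92 for week 14.

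**Dose on each day of the window:**

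- Week 13, days 81-89: 200 mg on four days (81-84), then 150, 150, 100, 100, 50. Four of nine days are at full dose and five are in the taper.
- Week 14, days 88-96, assuming the same +/- 4 days: 100, 50, 50, then 0 on six days.

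**Relative level.** One compartment with constant input over each day (an assumption). The daily retention factor is r = 2^(-24/21) = 0.453. With L the level at the start of the day, relative to steady state on 200 mg/day:

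L(next day) = r x L + (1 - r) x dose/200

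Example: L(86) = 0.453 x 1 + 0.547 x 0.75 = 0.863.

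| Day | 81-85 | 86 | 87 | 88 | 89 | 90 | 91 | 92 | 96 |
|---|---|---|---|---|---|---|---|---|---|
| Level | 1.00 | 0.86 | 0.80 | 0.64 | 0.56 | 0.39 | 0.31 | 0.14 | 0.006 |

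**Averages, visits spread evenly over the window (an assumption):**

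- Week 13: (5 x 1 + 0.863 + 0.801 + 0.636 + 0.562)/9 = 7.862/9 = 0.87.
- Week 14: days 88-92 sum to 0.636 + 0.562 + 0.391 + 0.314 + 0.142 = 2.045. Multiplying by 0.453 each day gives 0.064, 0.029, 0.013 and 0.006 for days 93-96, sum 0.112. The mean is 2.157/9 = 0.24.

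If the effect is proportional to level, average dilution is 1 - 0.87 = 13% on week 13 and 1 - 0.24 = 76% on week 14.

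**Where an unambiguous test could sit.** Visit 9 at day 78 +/- 4 spans days 74-82, all scheduled at 200 mg/day and following 42 scheduled days at that dosage. Sections 1.5 and 6.10 label Visit 9 as week 11. On that label it is day 71 +/- 4, days 67-75, which is also wholly at 200 mg/day. Visit 6 (day 36) would not serve, because the previous day's scheduled dose is 150 mg.

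**The case against.** The strongest reply is that week 13 has more textual support and leaves little dilution. It appears in both parts of Table 2 and in the heading and text of 6.5. The payment table in 12.3 also fits: daily calls are paid for 5 + 2 + 2 + 2 = 11 weeks through Visit 9 and one week at Visit 10, 12 in all, which puts Visit 10 about a week after Visit 9. Table 1's second column is headed as medication dispensed and, for the treatment visits, gives the period the supply covers, so its week-14 entry could mean the first period without drug. On this view the modelled level is about 100% at the nominal day and never below about 56% in the window. This stands as to size. It does not remove the variation between subjects or the conflict between the tables.

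A second reply is that these are exploratory measures with cover elsewhere. Neither test is a listed endpoint in 3.2-3.4, and section 7 has no analysis for them. The adverse-events checklist is given at every treatment visit, and the medication groups are compared on it. CogState tests working memory 6-8 weeks after first dose in the MRI sub-study (planned 100 subjects). All of this stands, with limits: the checklist records complaints rather than performance, the sub-study is optional, and CogState as described has no verbal fluency task.

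A third reply is that exposure at Visit 10 can be approximated from dispensing records and returned medication. That is partly so. But the daily calls run for 12 weeks and do not cover the taper, and a correction for exposure would rest on a model where a test before the taper needs none.

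A reader might also infer that the endpoint SIP, GGTP, %dCDT, AUQ and MED-Q are materially harmed by the two dates. The documents show no such consequence, and the point is not made here.

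**Conclusion.** The scheduling gap and the conflict over Visit 10 are both real. Neither test is scheduled where subjects are unambiguously on maintenance dosing, although both were chosen to examine the drug's effects. The dilution is modest on the week-13 reading (about 13% on average) and heavy on the week-14 reading (about 76%). Those figures assume one-compartment kinetics with constant daily input, visits spread evenly over the window, the same window for week 14, the scheduled dosage taken as planned, and an effect proportional to level. Subjects on reduced dosages, and early withdrawals who receive the endpoint battery when they withdraw (6.5), add further variation in exposure.

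A reader might infer that Visit 10 captures almost none of the cognitive effect, or that a null result there would falsely establish cognitive safety. The documents do not support either as a general statement. With week 13 counted from its start, as the other visits are, near-zero levels arise only from the week-14 entry, and these two tests are not the only cognitive data collected. The analysis of heavy drinking days is not touched. This is a cheap improvement worth making.

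**What to change.** - Add COWA and Digit Span to Visit 9 in Table 2 and in the 6.4.1 assessment list, before the taper begins.
- State that the screening-to-Visit 9 change, compared between medication groups, is the exploratory drug-effect comparison. Keep Visit 10 and the follow-ups as measures of recovery.
- Reconcile the week of Visit 10 across Table 1, Table 2 and section 6.5, and say where the visit falls relative to the taper. The week label for Visit 9 in sections 1.5 and 6.10 can be aligned in the same amendment.

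This changes no dosing, sample size or primary analysis. Section 6.2 puts COWA at about 5 minutes. It gives no time for Digit Span, which is assumed here to be similarly short. The other cost is one more practice exposure, which is the same in both arms.

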6.3 Visit 1 (Week 1; Baseline and First Treatment Visits)

Subjects will be informed of their eligibility status within 5 days and scheduled for a baseline assessment within 30 days of the screening visit. All subjects not eligible for the study will be referred to the appropriate treatment center or other research study. Eligible subjects will undergo a **baseline** research evaluation (lasting up to 2 hours) within 30 days of completing the screening visit.

Subjects will be asked to complete a breathalyzer test. If a subject's breath alcohol concentration is $\geq 0.02\%$, an investigator will evaluate whether the subject is too impaired to complete the study assessments. The study visit may be completed at the discretion of the investigator. If the subject is deemed to be unable to complete assessments, the investigator may ask the subject to wait until his or her blood alcohol level decreases or if that is not feasible to return the next day after having consumed no alcohol. Prior to discharge from the TRC, a clinician will assess the subject to ensure that it is safe for the subject to leave. Study staff will complete the following assessments with all subjects (the exception being that only for women of childbearing potential, will study staff obtain a urine sample for a pregnancy test).

- The Patient Health Questionnaire (PHQ-9), a validated 9-item self-report measure of depressive symptoms that yields a total score of 0-27 (Kroenke, Spitzer et al. 2001), will be administered at each visit.
- The International Neuropsychiatric Interview 6.0 (Mini 6): Suicidal risk will be assessed using the MINI Suicidality section (B) at each study visit and, if rated greater or equal to 9 (i.e., clinically significant suicidal ideation), the physician will be consulted to decide on the appropriate clinical management.
- Daily Interactive Voice Response (IVR) Telephone Call (daily for 12 weeks, beginning with the initiation of treatment)
 - a. Drinking diary: Every evening, as part of the daily IVR diary report, subjects will record their alcohol consumption by reporting the number of standard drinks of beer, wine, liquor and "other" category. The daily assessment will also include the number of cigarettes smoked that day. To capture all drinking during the preceding 24-hour period, subjects are asked to report separately drinking from yesterday (in total), and any drinking during the current day, up until the time of the IVR report. This will allow us to examine lagged associations (Kranzler, Armeli et al. 2013) The time of the calls (5-8 PM) was chosen to minimize the potential for subjects to have begun drinking heavily prior to making the calls. Subjects are taught to complete the telephone interview, which requires less than 5 minutes/day. Daily measures of alcohol consumption obtained via IVR will enable us to examine co-variation of alcohol-related subjective reports and drinking behavior to test for moderator effects.
 - b. Daily medication usage: Subjects will use Interactive Voice Response (IVR) daily to report whether they took their medication as prescribed. We previously found that subjects used the IVR system to report their use of medication that day,

CONFIDENTIAL

which correlates highly ($r=0.91$) with electronic monitoring (i.e., MEMS cap) (Feinn, Tennen et al. 2003).

c. Subjective Reports

- i. Daily mood: Patients will be asked to rate their overall mood daily during the 12 weeks of active treatment using an adjective checklist. The checklist consists of 4 mood adjectives, each of which will be rated on a 5-point scale (0 = "not at all" to 4 = "extremely"). The items will measure unpleasant (*sad, angry, nervous*) and pleasant (*happy*) mood.
 - ii. Expectancies of the effects of alcohol: These will include 4 items assessing anticipated positive ($n=3$) and negative ($n=1$) outcomes for drinking later that day. The positive expectancy items, adapted from existing expectancy scales (Rohsenow 1983; Fromme, Stroot et al. 1993; Leigh and Stacy 1993), correspond to the commonly identified expectancy domains of general pleasure, tension reduction, and social expressiveness. Specifically, subjects will be asked "If you were to drink tonight how likely is it that you" (a) "would have a good time?", (b) "would feel less tense/more relaxed?", and (c) "would be more outgoing/friendly? The negative expectancy item will be "would you get sick or have a hangover later?" Responses will be made on a 5-point.
 - iii. Thoughts about drinking: Based on anecdotal reports by subjects that topiramate substantially reduced the extent to which they thought about drinking (which they differentiated from desire to drink), they will be asked to rate this measure daily on a 5-point scale.
 - iv. Self-efficacy: We will measure both confidence to avoid drinking and confidence to resist heavy drinking on a 5-point scale.
 - v. Desire to drink: We will measure desire to drink using three items from the Alcohol Urge Questionnaire (Bohn, Krahn et al. 1995), which will be rated on a 5-point scale
 - vi. Experience of an alcohol-induced blackout: We will ascertain whether the subject experienced an alcohol-induced blackout using the following yes/no questions: (a) "Since your last call, after or while you were drinking alcohol, did you experience a period of time that you could not remember things you said or did? (b) (Follow-up question if the person responds yes): "When you experienced difficulty remembering something you said or did while drinking, did you later remember when given cues or reminders about it?"
- Medication Adverse Effects Checklist: Subjects will be interviewed by the study nurse and asked to report adverse effects at each study visit using a checklist of adverse medication effects derived from completed studies of topiramate for alcohol treatment. This method worked well in our completed trial using the 200-mg/day dosage (Kranzler, Covault et al. 2014).
 - Measures of treatment received: Records of medication taken will be kept and subjects will be asked to return the unused portion of study medication at each visit. The nurse will also record the number of contact hours subjects have been exposed to any alcohol treatment outside of the study.
 - The Short Index of Problems (SIP). The SIP, a 15-item instrument subset of the 50-item DrInC (Miller, 1995), measures alcohol dependence symptoms and medical, psychological,

CONFIDENTIAL

social, occupational, and legal problems. This shorter questionnaire reduces respondent burden (Feinn, Tennen et al., 2003b).

- The RAND 12-Item Health Survey (SF-12) (Ware Jr, Kosinski et al. 1996), a self-report measure of life functioning in various domains, will be completed at study baseline and endpoint. We will focus on the mental health component of the SF-12.
- Alcohol Urge Questionnaire (AUQ) (Bohn, Krahn et al. 1995) is an 8-item, self-administered state measure assessing the urge for an alcoholic drink at the time the questionnaire is completed and provides an index of acute craving. The AUQ contains four items pertaining to the desire to drink: two items regarding expectations of positive effects from drinking, and two items relating to the inability to avoid drinking if alcohol were present. This measure has strong correlations with measures of alcohol dependence and severity.
- The Clinical Institute Withdrawal Assessment for Alcohol Scale–revised (CIWA-Ar) (Sullivan, Sykora et al. 1989) is a 10-item scale for clinical quantification of the severity of alcohol withdrawal.
- Composite Scale of Morningness (CSM) is a 13-item survey that assesses whether the participant is most alert in the morning or later in the day, e.g. an “owl” or a “lark.” (Smith, Reilly et al. 1989)
- Insomnia Severity Index (ISI) is a five-item questionnaire that assesses the quality of sleep and its effect on activities of daily living. (Bastien, Vallieres et al. 2001)

Study staff will train subjects to use the IVR phone system. Subjects will be instructed on when to call in each day and how to use the phone system to complete the daily assessment. They will receive a written copy of the directions with all of the questions and responses. Study staff will program subjects’ study identification number into the IVR phone system after they have been randomized to study medication.

Subjects will receive the first counseling session and study medication (topiramate or placebo) during the **first treatment session** scheduled on the same day as the baseline assessment (after all assessments have been completed). At this visit, the subject will also meet with the physician. At this (and every) visit, the study nurse experienced in the use of Medical Management in alcohol pharmacotherapy trials will use the method to counsel the subject. This provides a basic clinical intervention that was designed to be used in conjunction with prescribed medication, and to be easily implemented by medically trained practitioners in non-specialty settings. The treatment will support subjects’ efforts to stop or reduce their drinking, with the study nurse making direct recommendations for reducing drinking to sensible levels.

The first counseling session (which will last approximately 30 minutes) will consist of a review of the results of the initial evaluation, identifying any concerns the subject may have. The subject is then provided with a rationale and information about pharmacotherapy and the importance of adherence. Subsequent treatment sessions (approximately 20 minutes) will be conducted at each treatment visit. During these sessions, the study nurse will obtain the subjects’ vital signs and weight, ask about medication side effects and concurrent medications, perform a brief assessment of the subjects’ drinking and medication adherence, and in some cases, make recommendations on strategies for the subject to follow until the next visit. Men will be advised to consume no more than 3 standard drinks per day and 12 standard drinks per week and women will be advised to consume no more than 2 drinks per day and 8 drinks per week. Because subjects will not be physically dependent on alcohol, reduction of heavy drinking is a safe and ethical goal.

CONFIDENTIAL

The physician will meet with the subject at the beginning of treatment and discuss clinical management with the study staff weekly. The physician will evaluate the subject for any severe or persistent adverse effects.

